8.3 Economic health assessment

An assessment of the duration of health-related temporary disability will be made based on the collected data (number of hospitalizations due to COPD exacerbations, outpatient visits concerning COPD) in the observational study.

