7. Collect data concerning the results of laboratory tests and instrumental examination methods confirming COPD diagnosis, present in the outpatient medical records (spirometry, specific complaints, haematology, instrumental examination methods)
8. Determine the patient's phenotype according to current classification
9. Collect data concerning adverse drug reactions
10. Complete the CRF.

Table 1. Visit schedule

Procedures	Visit "Enrolment"
Timelines	At the moment of enrolment into the registry
Inclusion / exclusion criteria	X
COPD. Severity grade, reversibility of airway obstruction (according to spirometry results*)	X
Demographics (year of birth, ethnicity, gender),	X
Socioeconomic status (education, occupation)	X
Smoking status	X
Occupational status, including information regarding the number of days of disability in the past 1 year.	X
Height, Weight, BMI (if applicable)	X
Comorbidities and clinical characteristics	X
Number of exacerbations COPD	X
Number of outpatient visits concerning COPD per year	X
Mean number of hospitalizations due to COPD	X
Determination of patient's phenotype according to current classification	X
Medical history concerning prior treatment of COPD	X
Medical history concerning treatment of COPD in the year prior to enrolment	X
Collection of data regarding changes in regimens of COPD treatment in the year prior to enrolment	X
Information concerning new complaints	
Spirometry. Results evolution (if applicable*)	X
Chest X-ray examination (if applicable*)	X*
Eosinophilia (eosinophil blood count based on haematology (Data of Le, EOS in % and in cells per μ l (haematology)	X
Pulse oximetry (if applicable*)	X*
Adverse drug reactions	X
CRF completion	

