7. STUDY CONDUCTION

7.1 Description of the visits

Visit "Enrolment". At this visit the patients will be enrolled into the study. De-identified data are entered retrospectively based on analysis of the outpatient medical records.

At this visit the Physician-investigator will complete the following information (collected retrospectively):

1. Verify inclusion/exclusion criteria
2. Establish the date of COPD diagnosis
3. Collect medical history concerning significant comorbidities and clinical characteristics, rate of exacerbations, pneumonia cases, hospitalizations, number of emergency calls, number of outpatient visits concerning COPD, number of days of disability in the year prior to enrolment
4. Evaluate smoking status. Wherever possible, smoking in pack-years
5. Collect medical history concerning treatment regimens, including different regimens of CS use, which the patient took/was prescribed in the year prior to enrolment into the registry (trade name of the medicinal product and INN, doses, dosing regimen, duration of use)
6. Collect demographic data and information concerning the patient's socioeconomic status
7. Collect data concerning the results of laboratory tests and instrumental examination methods confirming COPD diagnosis, present in the outpatient medical records (spirometry, specific complaints, haematology, instrumental examination methods)
8. Determine the patient's phenotype according to current classification
9. Collect data concerning adverse drug reactions
10. Complete the CRF.

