8.2 Secondary endpoints

1. Percentage (%) of patients with different disease phenotypes among outpatients
2. Percentage (%) of prescriptions of medicinal products to COPD patients which are in line with their disease severity according to Federal clinical guidelines for diagnosis and treatment of COPD patients, 2014
3. Distribution (%) of COPD patients who seek attention from primary medical care physicians by severity of airway obstruction (according to Federal clinical guidelines for diagnosis and treatment of COPD patients, 2014)
4. Mean number of exacerbations requiring medical attention (outpatient prescription of oral corticosteroids CS and/or antibiotics) in the last year in COPD patients
5. Mean number of hospitalizations in the last year in COPD patients
6. Mean duration (seriousness) of a temporary disability case. Number of days of temporary disability /Number of cases of temporary disability (reference form 16-BH)
7. Percentage (%) of COPD patients who received different regimens for treatment of COPD, including short-acting muscarinic antagonist (SAMA), short-acting β_2 -agonists (SABA), long-acting β_2 -agonists (LABA), long-acting muscarinic antagonist (LAMA),

oral corticosteroids (oral CS), fixed dose combination (FDC), phosphodiesterase-4 inhibitor, theophylline for the past year

8. Percentage (%) prescriptions to COPD patients which are in line with their disease severity according to GOLD classification and Federal clinical guidelines for treatment choice
9. Percentage (%) of patients with eosinophilic inflammation (eosinophil count according to haematology $>2\%$, $>3\%$, $>4\%$ or equivalent to absolute counts of >200 , >300 , >400 cells per μl)
10. Percentage of patients receiving sufficient extent of treatment in line with disease severity according to Federal clinical guidelines for diagnosis and treatment of COPD patients, 2014
11. Disease burden based on the collected data concerning the duration of temporary disability, number of hospitalizations due to COPD exacerbations, outpatient visits concerning COPD during follow-up

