8.3.1 Disease burden assessment

An assessment of the duration of health-related temporary disability will be made based on the collected data (number of hospitalizations due to COPD exacerbations, outpatient visits concerning COPD) in the observational study.

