12.2 Description of endpoints

Primary endpoints

1. Description of the clinical profile of COPD patient under outpatient treatment/surveillance at outpatient polyclinic healthcare institutions of the Russian Federation in Moscow

Secondary endpoints

1. Percentage (%) of patients with different disease phenotypes among outpatients
2. Percentage (%) of prescriptions of medicinal products to COPD patients which are in line with their disease severity according to Federal clinical guidelines for diagnosis and treatment of COPD patients, 2014
3. Distribution (%) of COPD patients who seek attention from primary medical care physicians by severity of airway obstruction (according to Federal clinical guidelines for diagnosis and treatment of COPD patients, 2014)
4. Mean number of exacerbations requiring medical attention (outpatient prescription of oral corticosteroids CS and/or antibiotics) in the last year in COPD patients
5. Mean number of hospitalizations in the last year in COPD patients
6. Mean duration (seriousness) of a temporary disability case. Number of days of temporary disability /Number of cases of temporary disability (reference form 16-BH)
7. Percentage (%) of COPD patients who received different regimens for treatment of COPD, including short-acting muscarinic antagonist (SAMA), short-acting β_2 -agonists

(SABA), long-acting β_2 -agonists (LABA), long-acting muscarinic antagonist (LAMA), oral corticosteroids (oral CS), fixed dose combination (FDC), phosphodiesterase-4 inhibitor, theophylline for the past year

8. Percentage (%) prescriptions to COPD patients which are in line with their disease severity according to GOLD classification and Federal clinical guidelines for treatment choice
9. Percentage (%) of patients with eosinophilic inflammation (eosinophil count according to haematology $>2\%$, $>3\%$, $>4\%$ or equivalent to absolute counts of >200 , >300 , >400 cells per μl)
10. Percentage of patients receiving sufficient extent of treatment in line with disease severity according to Federal clinical guidelines
11. Disease burden based on the collected data concerning the duration of temporary disability, number of hospitalizations due to COPD exacerbations, outpatient visits concerning COPD during follow-up

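### Secondary endpoint 6 divides disability days by disability cases, but no case count is listed for collection, and Sections 8.3 and 8.3.1 name the wrong data source for disability duration

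*Combined protocol and SAP*

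**What the plan says.** Sections 8.2 and 12.2 both list secondary endpoint 6 as "Mean duration (seriousness) of a temporary disability case" and define it as "Number of days of temporary disability /Number of cases of temporary disability (reference form 16-BH"). Endpoint 11 begins "Disease burden based on the collected data concerning the duration of temporary disability, number of hospitalizations due to COPD exacerbations, outpatient visits concerning COPD during" and closes with a reference to follow-up, so disability duration stands there as its own item beside admissions and visits.

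On collection, Table 1 has a row reading "Occupational status, including information regarding the number of days of disability in the past 1 year". Item 3 of the enrolment procedures in Section 7.1 ends with "number of outpatient visits concerning COPD, number of days of disability in the year prior to enrolment"; item 3 in Section 3 asks for the same days item.

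On derivation, Section 8.3 states: "An assessment of the duration of health-related temporary disability will be made based on the collected data (number of hospitalizations due to COPD exacerbations", with outpatient visits as the other named source. Section 8.3.1 repeats the sentence, ending "number of hospitalizations due to COPD exacerbations, outpatient visits concerning COPD) in the observational study". Section 8.3.2 says that no further burden parameters will be evaluated. Section 12.4 specifies descriptive statistics and gives no rule on denominators.

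**The concern.** Endpoint 6 needs two inputs, and the collection lists supply one. If the CRF follows those lists, the analyst at database lock will hold total days per patient and nothing to divide by.

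Separately, an analyst who follows Section 8.3 literally would try to obtain days off work from counts of admissions and visits. Those counts cannot give a duration: an admission may be short or long, and a visit may or may not lead to a certificate.

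Temporary disability is a named component of secondary objective 7 and enters endpoints 6 and 11. At stake is whether one secondary endpoint can be reported at all, and whether the disability part of the burden description comes from the right data.

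**Working it through.** The plan gives no expected disability figure and no calculated sample size, so there is no stated number to reproduce. The check compares what each endpoint needs with what is listed, followed by simple ratios.

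**1. Inputs needed and inputs listed**

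| Quantity | Needed for | Section 3, item 3 | Section 7.1, item 3 | Table 1 |
|---|---|---|---|---|
| Disability days, past year | Endpoints 6 and 11 | Listed | Listed | Listed |
| Number of disability cases | Endpoint 6 | Not listed | Not listed | Not listed |
| Start and end dates of cases | Endpoint 6, as a substitute | Not listed | Not listed | Not listed |

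Form 16-BH is cited in the endpoint definition as a reference; no collection list names it as a source of data.

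**2. Do days alone fix endpoint 6?** Days per case = days / cases. For a patient with 30 days in the year (assumed for illustration):

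- 1 case: 30/1 = 30 days per case
- 2 cases: 30/2 = 15
- 3 cases: 30/3 = 10

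The same recorded total fits a threefold range, so the days item does not determine the endpoint.

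**3. Do Sections 8.3 and 8.3.1 agree with the rest?** They name admissions and visits as the basis for duration. Table 1 and Sections 3 and 7.1 collect days directly, and endpoint 11 treats duration as separate from admissions and visits. These passages conflict, but the days themselves are available.

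**4. Does the share of patients in work matter?** Assume 2000 patients, 0.5 cases per working patient per year, 14 days per case, and a working share w. Then cases = 2000 × w × 0.5 and days = cases × 14.

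| w | Workers | Cases | Days | Days per case | Days per patient, all 2000 | Days per worker |
|---|---|---|---|---|---|---|
| 0.2 | 400 | 200 | 2800 | 14.0 | 1.4 | 7.0 |
| 0.4 | 800 | 400 | 5600 | 14.0 | 2.8 | 7.0 |
| 0.6 | 1200 | 600 | 8400 | 14.0 | 4.2 | 7.0 |

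Non-working patients add neither days nor cases, so endpoint 6 does not move. Only a per-patient mean depends on w, which makes this a matter for endpoint 11. There the plan states no denominator.

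**5. Do the wordings match?** The endpoints say temporary disability; the collected item says disability. In the procedure lists, visits are tied to COPD and disability days are not. A case count limited to COPD, set under days from any cause, would overstate the length of a case.

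**The case against.** The best defence is that the CRF is not among the documents. Endpoint 6 itself names the number of cases, so the field may exist. That stands as a limit on wording: the count is not listed in Sections 3 and 7.1 or Table 1, which is weaker than saying that it is not collected. It does not remove the need to list it.

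The sentence in 8.3 may also be a garbled form of the three burden items in objective 7, with days meant to come from the days field. That is plausible, and for this reason the duration is not lost. The text as it stands still directs the analyst to inputs that cannot give days.

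Endpoint 6 is one of eleven secondary endpoints in a descriptive study without a hypothesis, and the synopsis does not list it among its variables. That limits the weight of the point but does not make the endpoint calculable.

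A reader might go further and infer that non-working patients dilute the disability endpoints and hide differences between severity grades. The documents do not support this. Endpoint 6 divides by cases, no passage places non-working patients in any denominator, Table 1 records occupational status, and no comparison of disability by severity grade is planned.

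**Conclusion.** The point holds for endpoint 6: from the listed data its denominator is missing, and days alone leave it undetermined (30, 15 or 10 days per case in the example). It also holds that Sections 8.3 and 8.3.1 conflict with the collection lists and with endpoint 11 and must be reconciled with them.

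It would be too strong to conclude that the temporary-disability endpoints as a group cannot be produced. Days are collected, so the duration component of endpoint 11 can be reported. What is open there is the denominator of any per-patient summary. On the assumptions in step 4, an all-patient mean would lie between 1.4 and 4.2 days against 7.0 per working patient. Those figures show direction only, since the documents give no employment share, case rate or case length.

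The conclusion on endpoint 6 assumes that the CRF follows the procedure lists and Table 1. If the CRF already records cases, what remains is a correction of the protocol text.

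**What to change.** 1. **Case count.** Add the number of temporary disability cases in the year before enrolment to Sections 3 and 7.1, Table 1 and, if absent, the CRF. State whether days and cases are COPD-related or all-cause, and use the same cause and the same one-year window for both. Word the days item as temporary disability. Compute endpoint 6 as total days over total cases among patients with both recorded, and report how many patients that is. If cases cannot be retrieved for records already abstracted, restate endpoint 6 as days per patient; item 3 then applies to it as well.
2. **Sections 8.3 and 8.3.1.** Replace the sentence so that disability duration comes from the recorded days and cases, with admissions and visits reported as separate burden items.
3. **Endpoint 11.** State the denominator of any per-patient disability summary. Also report days per patient who worked at any time in that year, beside the percentage working. Table 1 is completed at enrolment, so the occupational item must cover work during the year; otherwise a patient who stopped work would be dropped although days were recorded. This does not affect endpoint 6 as now defined.

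**Cost.** One added field, drawn from the outpatient records where they hold it. Version 3.0 is dated March 2018 and last enrolment is planned for the second quarter of 2018, so some records already entered would need re-abstraction. Section 10.1 requires written ethics approval before an amended protocol or CRF is used. The mean among working patients rests on a smaller group and is less precise.

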8.3.1 Disease burden assessment

An assessment of the duration of health-related temporary disability will be made based on the collected data (number of hospitalizations due to COPD exacerbations, outpatient visits concerning COPD) in the observational study.

8.3.2 Other parameters for disease burden assessment

No other parameters will be evaluated as part of this Protocol.

9. SAFETY ASSESSMENT

9.1 Definitions

9.1.1 Definition of an adverse event (AE)

Adverse event (AE) is defined as any untoward medical occurrence in a patient or clinical study/trial subject administered a pharmaceutical/investigational medicinal product and which does not necessarily have a causal relationship with this treatment.

Adverse event can be any unfavourable symptom (e.g. nausea, chest pain) and unintended sign (e.g. tachycardia, enlarged liver) or an abnormal result of investigation (e.g. abnormal laboratory finding, electrocardiogram)

The AE definition is used both for serious and non-serious adverse events to regulatory authorities of the Russian Federation.

Furthermore the following events are subject to registration and Investigator is responsible for reporting the medicinal product safety related information to the regulatory authorities of the Russian Federation including but not limited: reports regarding administration of the medicinal product during pregnancy and/or lactation, drug interactions, lack of therapeutic effect, overdose, abuse, misuse, off-label use, suicide attempt or suicide death

9.1.2 Definition of a serious adverse event (SAE)

Any untoward medical occurrence that at any dose of the medicinal product:

- results in death;
- is life-threatening;
- requires inpatient hospitalization or prolongation of existing hospitalization;
- results in persistent or significant disability/incapacity;
- is a congenital anomaly/birth defect;
- is any other clinically significant medical occurrence which may threaten the patient or require medical attention.

NOTE.

- The term "life-threatening" refers to any event during which there is a risk of death for the patient; it does not refer to an event which hypothetically could have led to a lethal outcome if it were more severe.

Medical occurrences of special interest, but not resulting in death or life-threatening events or requiring hospitalization, can also be considered serious adverse events in those cases when according to medical and scientific judgement they might jeopardise the patient (or patients) and might require therapeutic or surgical intervention to prevent one of the other outcomes listed above. Any suspected transmission via a medicinal product of an infectious agent is also considered an SAE. Any organism, virus or infectious particle (for example Prion Protein Transmitting Transmissible Spongiform Encephalopathy), pathogenic or non-pathogenic, is considered an infectious agent. In such case these events are regarded as serious. Examples of such events are advanced or malignant tumour, intensive treatment in an emergency room or at home for allergic bronchospasm, blood dyscrasias or convulsions that do not result in hospitalization, or development of dependency, or drug abuse.

9.2 Non-interventional studies without specific safety assessment objectives

As the present study is non-interventional, there will be no proactive collection of any safety data. All the reports concerning events associated with safety of medicinal products will be reported in line with pharmacovigilance regulatory requirements in the post-marketing period as spontaneous adverse event reports. It is crucial that all the employees participating in the study are aware of the contents of this section. The Principal Investigator or a designated

authorized representative is responsible for AE reporting to regulatory authorities in according local regulations and timelines, ensure that all the site employees participating in the study aware about the procedures for handling of spontaneous reports (the term spontaneous reports implies reports associated with safety of medicinal products), and also national pharmacovigilance regulatory requirements in Russia.

9.3 Non-interventional studies with specific safety assessment objectives

As the present study is non-interventional, there will be no proactive collection of any safety data.

9.4 Safety data reporting

9.4.1 Adverse event reports

Monitoring of the safety relation information of the investigation medicinal products should be performed according to the local pharmacovigilance requirements to standard medical practice in the territory of the Russian legislation.

9.4.2 Reports of unexpected adverse events during use of medicinal products for human use

As the present study does not stipulate any investigational medicinal product or vaccine, and includes only observation of patients receiving standard treatment with medicinal products approved for use in the territory of the Russian Federation, safety monitoring and reports regarding adverse events (including unexpected events) will be performed according to local pharmacovigilance requirements to standard medical practice in the territory of the Russian Federation.

9.4.3 Registration of spontaneous reports regarding adverse events

The following principles should be applied in case of registration of adverse events in study participants: the investigator should report adverse events per pharmacovigilance procedures according to local regulatory requirements:

1. To the Federal Service for Surveillance in Healthcare: In writing to the following address: [name]. A specific form should be used currently available at:
<http://www.roszdravnadzor.ru/i/upload/files/1308641445.19876-26263.doc>
2. To the corresponding pharmaceutical company, i.e. the marketing authorization holder of the appropriate medicinal product, according to local regulatory requirements.

10. ETHICS

This non-interventional multicenter study will be conducted in compliance with the Protocol, the Declaration of Helsinki, ICH GCP guideline, GEP and all the current local legislative requirements to conduction of non-interventional studies.

Physicians will conduct this non-interventional multicenter study in line with all current regulatory and legislative requirements to routine medical practice in the Russian Federation.

10.1 Committee on ethical review for clinical studies (EC)

Before study start, written favourable conclusion of EC (ethics committee) should be received concerning the study protocol, ICF and CRF. If in the course of the study any amendments to these documents are made, written approval should be received before their implementation.

10.2 Informed consent

The present study is retrospective and thus based on data which will be retrieved from archives kept by the investigators. Therefore, in this non-interventional study the choice of a specific therapeutic strategy for each patient has already been made and there is no need for prospective conduction of any additional diagnostic or monitoring procedures. Collection of patient data will be performed only by the personnel of the clinical institution; as these data will not include any information enabling identification of the patient, in the present study there is no need to obtain patient informed consent (according to the personal data protection law of the Russian Federation).

